Patients who are eligible and consented to the study will be randomly assigned, after completing the baseline measurement, to either Usual Care or the Intervention, in a 1:1 allocation ratio. Randomization will occur in blocks of 8, using random numbers. Randomization will be stratified by whether the study participant is newly placed on the waiting list (defined as placement on the waiting list <6 months prior to enrollment) or has already been on the waiting list (defined as placement on the waiting list ≥6 months prior to enrollment). Random number sequences will be generated by the off-site study biostatistician ([name]). To promote allocation concealment, the biostatistician will allocate study participants to their study arm at the time of randomization and inform the study coordinator of the assigned study arm. The study coordinator will contact potentially eligible transplant candidates by telephone to inform them of their assignment. Study participants and the study coordinator will be aware of allocation to Usual Care or the Intervention group, but outcomes assessors will be blinded to the allocation group.

Study aims & objectives

The primary aim will compare LDKT readiness and LDKT receipt in the Intervention vs. Usual Care groups of our randomized clinical trial. Our primary outcome is change in readiness to pursue LDKT, and our main secondary outcome is actual receipt of LDKT after 18 months of follow-up. Other secondary aims will determine (a) the social and behavioral variables that modify the effect of the Intervention upon LDKT readiness and receipt; and (b) whether the intervention affects other precursors of LDKT readiness and receipt, such as knowledge about LDKT, self-efficacy, and other social and behavioral factors.

Data collection, follow-up and outcomes

Baseline Measurements

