 - *Ways to more quickly receive a transplant.* In addition to encouraging LDKT, we will encourage study participants in the Intervention arm to consider the following ways to more quickly receive a DDKT: ●accept a high KDPI kidney, if deemed medically appropriate; ●accept a PHS increased risk kidney; ●get on the DDKT waiting list at other transplant centers outside New Jersey and the SBMC donation service area.

Destination Transplant Education Folder

As a supplement to the slide presentation, patients will be given a folder to take home that contains factsheets that provide an overview of the five types of kidney transplant. Although

the content varies between the factsheets, all factsheets provide patients with instructions or further directions on what to do if they are interested in pursuing a particular option.

Destination Transplant Postcards

During the 9-month intervention period, patients will be sent one educational postcard per month that serves to provide both basic information about kidney disease and additional information about the five treatment options. These colorful postcards feature real recipients and donors and tackle tough topics including asking someone to get tested as a donor. The 9 postcards address the following topics:

- *“Your Exploration of Kidney Transplant Continues at Home”*. Welcomes patients and provides a short list of recommendations for patients who are waiting for a transplant
- *“Consider All Types of Kidneys for Transplant”*. Encourages patients to consider nonstandard deceased donor transplant through use of High KDPI donor kidneys
- *“Consider All Types of Kidneys for Transplant”*. Encourages patients to consider nonstandard deceased donor transplant through use of Public Health Service Increased Risk donor kidneys
- *“Learn About Living Donation”*. Encourages patients to reach out to others for support and to consider living donor transplant as a treatment option
- *“Learn Why People Want to Be Living Donors”*. Presents reasons why living donors may offer to help out a friend or a loved one.
- *“Compare the Risks and Benefits of Living Donation”*. Provides information about the risks (including costs, future impact on health, and risk of death) associated with donating a kidney
- *“Consider Getting a Transplant from a Living Donor”*. Provides a list of strategies that may be used to help an individual identify a potential donor

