During the baseline assessment, patients will be asked some basic demographic and cultural questions such as their age, biological sex, race, and ethnicity. Clinical information will be collected, including data such as patient dialysis status and comorbidities such as diabetes, hypertension, and polycystic kidney disease.

Transplant derailers (baseline only)

Transplant derailers can be described as individual factors that might be sources of delay, difficulty, or challenge to a patient pursuing transplant. These factors include education, job status, income, health insurance quality, neighborhood/environmental assessment, financial stability, access to transportation, and family obligations.

Transplant knowledge & health literacy

To assess health literacy, the two-item subjective health literacy and numeracy measure was used⁴⁸. Extent of previous transplant education and current transplant knowledge measures were adapted from previously developed measures.⁴⁹ The knowledge and education measures were designed to assess the amount and quality of transplant knowledge participants had.

Small steps to pursue LDKT

Small steps include a list of actions that people may take related to getting a living donor transplant (e.g., talk to people you trust about whether to get a living donor transplant or ask potential donors to be tested).

Measures of readiness for LDKT, based upon TTM

We use previously validated scales⁴⁹ to measure readiness to pursue LDKT and the pros and cons of living donation. The readiness measures assess how ready patients are to take actions to pursue LDKT, based upon the stages in the Trans-Theoretical Model of Change (e.g. “I am not considering taking actions in the next six months to pursue living donation” (Pre-contemplation)). We also measured readiness using the scales developed by Rodrigue et al.²¹, which also measure readiness for LDKT but use slightly different wording (e.g. “I am not thinking about or considering live donor kidney transplantation” (Pre-contemplation) and “I have thought about live donor kidney transplantation and I am seriously considering the possibility” (Preparation)). The pros and cons assessment asks participants to rate the importance of a series of statements about transplant to their decision to pursue LDKT(e.g., “I will feel guilty having someone donate to me” or “With a living donor transplant, I will be able to contribute to my family and friends sooner”).

LDKT Decisional Balance and Self-efficacy

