Our initial analysis will be descriptive. Our main analysis will use standard intention-to-treat principles. First, we will describe participants’ baseline characteristics and compare

summary statistics of the Usual Care and Intervention groups. These summary statistics will include mean, standard deviation, median, and range for continuous variables, and counts and frequencies for categorical variables. Two-sample t-tests, Wilcoxon rank-sum tests (for non-parametric variables) and chi-squared tests will be used to test for differences between the Usual Care and Intervention groups, as appropriate.

For our primary outcome (increase in readiness to pursue LDKT), we will compare, using chi-square testing, the proportion of participants in the Usual Care vs. Intervention arms who have advanced at least one stage in their readiness to pursue LDKT (between the time of placement on waiting list and the time of reassessment at 18 months). For our main secondary outcome (receipt of LDKT), we will compare, using chi-square testing, the proportion of study participants in the Usual Care vs. Intervention arms who have received a LDKT. Sensitivity analyses will assess the intervention effect, adjusting for clustering of response by seminar group (because failing to account for clustering can reduce power)^{56,57}.

To determine which baseline factors (e.g. age), if any, modify the effect of the Intervention on the primary and secondary outcomes, logistic regression will model the log-odds of the outcome as a function of the intervention, while controlling for these factors of interest. Tests for modification by these key factors will be based on Wald tests of interaction terms between the intervention indicator and baseline factors. We will perform logistic regression⁵⁸ and model-building as we have in prior published analyses⁵⁹⁻⁶¹.

To test the effect of the intervention upon other precursors of LDKT readiness and receipt (e.g. knowledge about LDKT, self-efficacy, and other social and behavioral factors), we will use stratified chi-square tests for categorical variables and linear regression models for semi-continuous scales. The chi-square tests and linear regression models will be stratified by accumulated time on the waitlist at randomization (≤ 6 months vs. > 6 months). We will examine effects adjusted and unadjusted for baseline value for each respective scale.

Power and sample size calculations

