The proportion of Usual Care (control) patients who have increased readiness for LDKT could plausibly range from 0.10 to 0.40, while the proportion who receives a LDKT is expected to equal 0.14 (based on prior baseline data from our center). Assuming there are 250 or 200 (assuming 100% and 80% retention rates) participants in each group, powers for increases of 0.10, 0.15, and 0.20 are presented in Table 3. In most scenarios, we have >80% power to detect a clinically significant increase in LDKT readiness and receipt of LDKT. We may be slightly underpowered only for very small increases in these two outcomes. Clustering by seminar in the Intervention arm may slightly reduce our power^{56,57,62}, but we should have sufficient power to detect an effect of the Intervention upon our LDKT readiness and receipt.

Abbreviations

CKD: Chronic kidney disease;

DDKT: Deceased donor kidney transplant;

ESRD: End-stage renal disease;

KDPI: Kidney donor profile index;

KPD: Kidney paired donation;

LDKT: Living donor kidney transplant;

OPTN: Organ Procurement and Transplantation Network;

PHS: Public Health Service;

SBMC: Saint Barnabas Medical Center;

TTM: Transtheoretical Model of Behavioral Change;

References

4. U.S. Renal Data System. *2017 USRDS Annual Data Report: Epidemiology of kidney disease in the United States*. Bethesda, MD: National Institutes of Health, National Institute of Diabetes and Digestive and Kidney Diseases;2017.

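### The primary chi-square test ignores baseline readiness stage and scores falling back as staying, so it gives up power and cannot by itself tell a net rise from polarisation

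*Combined protocol and SAP*

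**What the plan says.** Under Study aims & objectives the plan states: "Our primary outcome is change in readiness to pursue LDKT". The measures section describes readiness as ordered stages, "based upon the stages in the Trans-Theoretical Model of Change". Under Statistical analyses this becomes a yes/no outcome: the two arms are set against each other, by a chi-square test, on the share of people "who have advanced at least one stage in their readiness to pursue LDKT".

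The same section gives adjustment for the baseline value, and stratified tests, only to the other precursors of readiness and transplant receipt. The one sensitivity analysis named concerns clustering by seminar. Wilcoxon tests appear only in the paragraph on describing and comparing the groups. There is no ordinal analysis of stage, no count of backward moves, and no rule for participants who start at the highest stage. Table 2 shows that stage is recorded at baseline and at both questionnaire follow-ups.

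For power, the control proportion "could plausibly range from 0.10 to 0.40", and the arm sizes are given as follows: "Assuming there are 250 or 200 (assuming 100% and 80% retention rates) participants in each group". Table 3 covers only the proportion moving up.

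**The concern.** Two features of the test matter.

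**Baseline stage is left out.** The chance of moving up depends on the starting stage and is zero at the top. Pooling all starting stages in one 2×2 table adds variation that the arms did not cause. Randomisation keeps the crude test valid, so this costs power and does not bias the result.

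**Backward moves are invisible.** A participant who drops a stage is scored like one who does not move. If the intervention moved some people up and others down, the proportion moving up could rise while readiness overall did not. A significant result could then be reported as increased readiness. The materials include a postcard that "Provides information about the risks (including costs, future impact on health, and risk of death) associated with donating a kidney", and they also promote faster routes to a deceased donor kidney, so movement away from living donation in some participants cannot be ruled out.

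**Working it through.** **1. The plan's own figure.** Alpha and sidedness are not stated; I assume two-sided 0.05. With n per arm and m = (p0 + p1)/2, the continuity-corrected power is

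Φ{ [ (p1 − p0) − 1/n − 1.96·√(2m(1 − m)/n) ] / √([p0(1 − p0) + p1(1 − p1)]/n) }.

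For 0.25 vs 0.40 at n = 200: m = 0.325; numerator 0.145 − 1.96 × 0.04684 = 0.0532; denominator 0.0462; ratio 1.15; power 0.875. Table 3 gives 0.88. At n = 250 the result is 0.939 against 0.94. All 18 entries agree within 2 points, so Table 3 is right for the endpoint as defined.

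**2. Assumed inputs for the simulations.** The documents give neither the number of stages nor the baseline mix nor any backward rate. I assume four stages and these control rows (from stage 1 to stage 4): [.60 .25 .10 .05], [.15 .50 .20 .15], [.05 .15 .50 .30], [.03 .07 .20 .70]. With a baseline mix of 20/30/30/20:

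- control moving up = 0.2×0.40 + 0.3×0.35 + 0.3×0.30 + 0.2×0 = 0.275, inside the plan's range
- control moving back = 0.3×0.15 + 0.3×0.20 + 0.2×0.30 = 0.165

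The second mix, 20/20/20/40, puts 40% at the top stage: 0.210 up and 0.190 back.

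**3. Tests compared, 200 per arm.** These are the planned chi-square on moved up or not; the same outcome by Mantel-Haenszel, stratified by baseline stage; and an ordinal test of follow-up stage stratified by baseline stage (van Elteren, tie-corrected). Each entry is the share of trials significant in favour of the intervention. A uniform shift multiplies the cumulative odds by e^0.5 = 1.65. In the forward-only rows the upward probabilities come from a shift of 0.5 (C) or 0.65 (D, E) in log-odds, and backward probabilities stay at control values. In row F, 19% of each stay share moves up and 15.5% moves back.

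| Scenario | Up, control → intervention | Back, control → intervention | Planned | Stratified | Ordinal |
|---|---|---|---|---|---|
| A. Uniform shift | 27.5% → 37.0% | 16.5% → 11.0% | 0.53 | 0.58 | 0.71 |
| B. Uniform shift, 40% at top | 21.0% → 28.2% | 19.0% → 12.8% | 0.38 | 0.46 | 0.69 |
| C. Forward only | 27.5% → 37.0% | 16.5% both | 0.53 | 0.58 | 0.39 |
| D. Forward only, larger | 27.5% → 40.0% | 16.5% both | 0.75 | 0.81 | 0.59 |
| E. Forward only, larger, 40% at top | 21.0% → 30.4% | 19.0% both | 0.57 | 0.69 | 0.41 |
| F. Polarised | 27.5% → 35.5% | 16.5% → 23.3% | 0.41 | 0.45 | 0.05 |

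Repeat runs differ by 0.01 to 0.02. With no effect, all three tests reject at about 2.5% on each side.

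**4. Reading the table.** In rows A to E, stratifying gains 5, 8, 5, 6 and 12 points. The ordinal test gains where backward moves also fall (A, B) and loses where they do not change (C, D, E). In row F the stratified test is no protection, because it tests the same endpoint; only a look at backward moves reveals what happened. With slightly more retreat (27.5% → 35.6% up, 16.5% → 25.2% back) the planned test favours the intervention in 42% of trials and the ordinal test in 3.5%.

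**5. The same point at a Table 3 step.** Suppose all moves are of one stage. Control 25% up and 10% back gives a mean change of 0.25 − 0.10 = +0.15. Intervention 40% up and 25% back gives 0.40 − 0.25 = +0.15, the same. The planned test declares benefit in 90% of trials at 200 per arm and 95% at 250; a rank test on stage change does so in 7% and 8%.

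**The case against.** The endpoint is a readable, prespecified responder measure. The introduction states the aim as an increase in readiness, and Table 3 is built on that proportion. Rejecting when the proportions moving up truly differ is not a type I error. This stands, and it is why the endpoint should stay.

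The backward mechanism is conjecture. The risk postcard is one of nine and sets out benefits as well; others, and the seminar's donor and recipient speakers, favour living donation. This also stands: the documents give no reason to expect retreat of the size in row F.

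A reader might infer that the ordinal test is more powerful whenever anyone moves back, and so should replace the chi-square. The documents do not support that, and rows C to E contradict it: backward movement is present throughout and the planned test is the stronger one. Nor can the ordinal power gain and the misleading positive result be argued together. The gain in A and B arises because retreat falls; the misleading result needs retreat to rise.

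Finally, the increases of 7 to 12.5 points in rows A to E are smaller than the step of 0.15 that Table 3 uses at a control rate of 0.25. At that step power is already 0.88 with 200 per arm, so stratification has less left to add.

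None of this answers the narrower point: a baseline variable that fixes the chance of success at zero for some participants is left out of the test, and backward moves are reported nowhere.

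**Conclusion.** The point holds in a limited form. The primary test is valid and Table 3 is correct for it. Leaving out baseline stage gives up about 5 to 12 points of power at 200 per arm in the scenarios with a real forward effect, and more when many participants start at the top. This rests on the assumed matrix and mixes; the gain disappears if the chance of moving up hardly varies by starting stage and few start at the top.

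Separately, a positive result shows that more intervention participants moved up. It does not by itself show that readiness rose overall. How often the two would diverge cannot be judged from the documents. A reader should not conclude that divergence is likely, that the planned result would be a false positive in the formal sense, or that an ordinal primary test is always better.

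**What to change.** - Keep moving up one stage or more as the primary endpoint. Test it stratified by baseline stage on the same readiness scale, by Mantel-Haenszel or by logistic regression with baseline stage as a covariate. State that participants at the top stage at baseline remain in the analysis and cannot advance.
- Prespecify a supportive ordinal analysis of follow-up stage stratified by baseline stage (van Elteren or proportional odds).
- Report by arm the proportions moving forward, unchanged and back, and those at the top stage at baseline.
- State that an overall increase in readiness will be claimed only if the primary result, the ordinal analysis and the table of moves agree.

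No new data are needed. The cost is revised analysis wording, slightly more analysis, and an adjusted estimate to report beside the crude difference in proportions. Table 3 can stand. The date of the follow-up stage must be settled separately: the analysis text places reassessment at 18 months, while Table 2 has no readiness measurement after 9 months.

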After active placement on the waiting list, we will obtain “baseline” measurements of multiple social and behavioral attributes, via telephone questionnaires of all patients enrolled in the study (see Figure for flow of patients through the study). If we are unable to administer the baseline questionnaires within 2 months of enrollment into the trial (e.g. within 2 months of placement on the waiting list for newly listed patients, or within 2 months of consent for the patients already on the DDKT waiting list), then we will not randomize the patient. This requirement is intended to minimize later study dropout. Study participants will be mailed a \$25 gift card for this baseline measurement.

Follow-up Measurements: Timing

Each Usual Care study participant will be matched to one Intervention participant. For patients randomized to the Intervention, we will administer a follow-up questionnaire by telephone, approximately 1 week after the Intervention. At the same time, we will contact the matched Usual Care patient to administer the follow-up questionnaire. This procedure will ensure that the post-Intervention follow-up questionnaires are administered at approximately the same time, post-listing, for both Usual Care and Intervention patients, and using the same modality (telephone). A final administration of the study questionnaires will occur at 9 months after randomization for patients in both arms. We will provide \$25 gift cards for each of these two follow-up measurements.

Standard of Care Components (Usual Care/Control Group)

Participants who are randomized to receive the Usual Care engage in the standard education and evaluation process given to all patients at SBMC. While on the waiting list, transplant candidates are asked to inform the transplant center of important changes in their medical condition (e.g. hospitalizations) but otherwise typically have infrequent contact with the transplant center. Candidates return to the transplant center for periodic reevaluations by

transplant staff, usually every 1-2 years, depending upon the transplant candidate's medical comorbidities. At these reevaluations, transplant personnel usually discuss LDKT. These Usual Care patients will receive usual concomitant care but no additional formal education.

Intervention Components (“Destination Transplant”)

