- “*You Can Get a Transplant Even if Your Donor is Not a Match for You*”. Defines and explains how Kidney Paired Donation works
- “*Weigh the Pros and Cons of All Your Options*”. Provides a side by side comparison of the pros and cons of dialysis, deceased donor transplant and living donor transplant

3 Months post-baseline follow-up coaching call

Approximately 3 months after the baseline assessment, patients in the intervention condition will receive a follow-up phone call from a coach (transplant research associate) to discuss topics including but not limited to:

- (1) their transplant plan and decision-making
- (2) what supports they have and/or need to ensure they are able to follow through with their transplant plan
- (3) how to discuss LDKT with friends and loved ones

The purpose of the call is to provide additional education and support for patients. These conversations also provide additional opportunity for patients to discuss their feelings about and willingness to pursue the various transplant options. This call serves as a mini-assessment wherein the coach assesses patient readiness to pursue LDKT. At the conclusion of the coaching call, patients are given the option to receive additional educational materials designed to help bolster their confidence in potential discussions about their need for an LDKT.

Patients expressing interest in learning more will be given the option to receive the *Explore Living Donation Packet* and the *Finding a Living Donor Booklet*. Each resource provides patients with practical, skills-based information to help initiate conversations about living donation. Through these materials patients will engage with videos and print materials that provide detailed descriptions about how others have found living donors. Additionally, patients

are given several sample letters that others have used with family and friends to help them identify potential donors.

Evaluation and Statistical Plan

Measures

Patient information was obtained, mainly via questionnaires, at baseline, interim follow-up (as explained above in *Follow-up Measurements: Timing*), and 9 months (Table 2).

Descriptions of these measures are below. Unless otherwise indicated, all measures were assessed at baseline, follow-up, and 9 months.

Demographic, clinical, and cultural factors (baseline only)

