This scale asks respondents to reflect on the information they received about their treatment options and reflect on the option they chose (e.g., I know the risks and side effects of each option and I have enough advice to make a choice).⁵⁵

18-Month Records Review

We will conduct a review of participants' medical records to assess transplant-related outcomes at 18 months post-randomization. These measures will include:

Receipt of LDKT

We will determine whether or not trial participants have received a LDKT in the United States during the 18 months after they were randomized. This determination will be made by examining our electronic medical records for each study participant. If the person received a LDKT within the U.S., then we will determine whether this LDKT occurred at SBMC or some other transplant center.

Recruitment of donor volunteers

Using electronic transplant medical records at SBMC, we will determine how many donor volunteers contacted the transplant center to donate to each study participant during the 18 month follow-up period. Persons are considered “donor volunteers” after they (1) contact the transplant program to request an information packet regarding live kidney donation, and (2) complete and return a Living Donor Referral Form (included in the packet) to SBMC.

Nursing education of donor volunteers

After returning the Donor Referral Form, donor volunteers must complete an in-person education session regarding live kidney donation. As the first step in the donor evaluation, appearance at the transplant center for this education is a sign of the “seriousness” of the donor volunteer’s intent to donate. For each study participant, we will determine how many (if any) of their donor volunteers appeared for an in-person nursing education session.

Status on the DDKT waiting list

We will determine the status of study participants still on the waiting list after the 18 month follow-up period. Specifically, we will determine whether they are: ●active (Status 1), or ●inactive (Status 7) on the waiting list. Other patients will have been removed from the SBMC waiting list because they: ●died; ●became too sick to transplant; ●refused transplant; ●transferred to another center; ●improved and no longer required transplant; ●received a DDKT; ●received a LDKT; or ●other. We will determine these reasons, along with the date they occurred, by querying the medical records for each patient.

Statistical analyses

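### The primary readiness comparison ends at an 18-month reassessment that is not in the collection schedule, and no collected visit is named as primary

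*Combined protocol and SAP*

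**What the plan says.** The Statistical analyses section makes the primary outcome an advance of one or more readiness stages, compared between arms by chi-square test. It measures the advance "between the time of placement on waiting list and the time of reassessment at 18 months".

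Other parts of the document bear on that time point:

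- *Study aims & objectives*: "Our primary outcome is change in readiness to pursue LDKT, and our main secondary outcome is actual receipt of LDKT after 18 months". The 18 months belongs to transplant receipt; readiness is given no time point.
- *Follow-up Measurements: Timing*: one questionnaire about a week after the seminar, with the matched Usual Care patient contacted at the same time, and then "A final administration of the study questionnaires will occur at 9 months after randomization for patients in both arms".
- *Measures*: "Unless otherwise indicated, all measures were assessed at baseline, follow-up, and 9 months". The readiness subsection states no exception.
- *18-Month Records Review*: this is a review of "medical records to assess transplant-related outcomes at 18 months post-randomization". Its listed items are transplant receipt, donor volunteers, their nursing education and waiting-list status.
- *Table 2*: the primary readiness row is marked at baseline, one week and nine months, and is blank at 18 months.
- *Randomization*: patients "will be randomly assigned, after completing the baseline measurement", so every randomized patient has a baseline questionnaire.

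**The concern.** The trial has one primary comparison, and its stated end point in time is one at which readiness is not measured. Whoever runs the analysis must replace 18 months with a visit that exists. Two are available in both arms, and they are not interchangeable. The one-week value is an early response to the seminar. The nine-month value also reflects the monthly postcards and the three-month coaching call, and falls at about the end of the programme: "During the 9-month intervention period, patients will be sent one educational postcard per month".

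The readiness scale is also open. The readiness subsection describes a first stage-based scale and then a second set of items "which also measure readiness for LDKT but use slightly different wording", without saying which one defines the primary outcome.

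If the visit is chosen after results by arm are known, the reported primary result may not be the planned one. From these documents alone a reader could not tell.

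**Working it through.** **1. Schedule against analysis rule**

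| Time | What is collected | Readiness, both arms? |
|---|---|---|
| Baseline, before randomization | Questionnaire | Yes |
| About 1 week after the seminar | Questionnaire | Yes |
| About 3 months | Coaching call | No, Intervention arm only |
| 9 months | Last questionnaire | Yes |
| 18 months | Records review | No |

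The analysis rule needs a value in the last row, where there is none. The power section assumes 200 to 250 per arm, so 0 of 2 × 200 = 400 to 2 × 250 = 500 participants would have one. The flow figure is not available to us, but the text and Table 2 agree with each other.

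**2. Does the power calculation settle the visit?**

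Table 3 can be reproduced with a continuity-corrected two-proportion formula at two-sided 0.05. The level is assumed, because the plan does not state it.

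Power = Φ{ [ |p₂ − p₁| − 1/n − 1.96·√(2p̄(1 − p̄)/n) ] / √[(p₁(1 − p₁) + p₂(1 − p₂))/n] }

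For 0.10 against 0.20 with n = 250:

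- Numerator: 0.100 − 0.004 − 1.96 × √(2 × 0.15 × 0.85/250) = 0.096 − 0.0626 = 0.0334
- Denominator: √((0.09 + 0.16)/250) = 0.0316
- Power: Φ(1.056) = 0.855, against 0.85 in Table 3

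With n = 200 the result is 0.760, against 0.76. The other cells also agree to within two points. The inputs are control rates of 0.10, 0.25 and 0.40 with no time attached. Table 3 is therefore sound on its own inputs and does not show which visit was meant.

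**3. Illustration of the open choice**

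Suppose there is no true effect, each visit is tested at |z| > 1.96, and either may be reported as primary. Treat the two statistics as bivariate normal with correlation ρ. The documents give no ρ, so these values are assumptions.

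| ρ | At least one significant, two-sided | At least one significant for benefit |
|---|---|---|
| 0.9 | 0.070 | 0.035 |
| 0.8 | 0.078 | 0.039 |
| 0.7 | 0.083 | 0.042 |
| 0.5 | 0.091 | 0.045 |
| 0.3 | 0.095 | 0.048 |
| 0 | 0.0975 | 0.049 |

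The nominal values are 0.05 and 0.025. At ρ = 0 the two-sided figure is 1 − 0.95² = 0.0975.

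Simulated chi-square tests on correlated binary outcomes, with 200 or 250 per arm and null rates of 0.10, 0.25 and 0.40, gave 0.068 to 0.072 at correlation 0.9 and 0.081 to 0.084 at 0.7. This confirms the normal approximation. It does not support any particular correlation.

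**The case against.** The best defence is that nine months was plainly meant. The analysis section points to a late assessment, nine months is the last questionnaire, and one week is a strained reading of 18 months. That makes nine months the likelier intention, but no section says so. The one-week visit is a deliberately matched between-arm assessment and is marked in the primary row of Table 2. Calling nine months the last administration describes the schedule; it does not name a primary visit.

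Four further points have some force:

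- The trial was registered before intervention activities began, and the registration may name a time point. We cannot see it, so the statement that a reader could not tell is limited to these documents.
- The plan nowhere proposes claiming success at either visit. The error rates illustrate what an undocumented choice could cost; they are not a property of the plan. The finding does not depend on them.
- The documents show a conflict, not which side of it is wrong. An 18-month questionnaire left out of the schedule is less likely but not excluded.
- The nine-month visit is timed from randomization, and the documents do not give the interval from randomization to the seminar. That it falls at the end of the intervention period is therefore approximate.

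None of this supplies a readiness value at 18 months or names a substitute.

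**Conclusion.** The concern holds. The primary analysis cannot be carried out as written, because the schedule yields no readiness value at 18 months for any participant, and the plan does not say which collected visit replaces it. This rests on the agreement of the timing section, the measures section, the records-review section and Table 2, and needs no numerical assumption. The illustrative error of about 7% to 8% two-sided (3.5% to 4.2% for benefit) does rest on assumed correlations of 0.9 to 0.7; lower correlations raise it, to at most 9.75% (4.9%) at independence. Because this is the single primary comparison, it must be fixed.

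**What to change.** In Statistical analyses, define the primary outcome as the proportion advancing at least one stage from the trial baseline questionnaire to one named, collected visit, on one named readiness scale.

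- **Visit.** Nine months is the natural candidate: it is the latest questionnaire and falls at about the end of the intervention period. The sponsor should confirm it. Make the one-week comparison secondary and keep 18 months for the records-based outcomes.
- **Scale.** The first-listed stage-of-change scale fits the Table 2 label, but both scales use stage wording, so the label alone does not decide. Name one and make the other secondary.
- **Start.** Replace waiting-list placement with the baseline questionnaire. Part of the sample was listed six months or more before enrollment, and baseline is the first readiness value every randomized patient has.
- **Anchor.** The text times the 9- and 18-month assessments from randomization, while Table 2 times both from baseline. Use one anchor throughout.
- **Timing of the decision.** Settle this before any unblinded analysis. If that has passed, state when and how the visit was chosen.

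The cost is one rewritten sentence and the timing labels in Table 2, with no new data. If the sponsor did intend an 18-month questionnaire, the schedule must be changed instead, and that would require further data collection.
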